## OVERALL DESIGN

As of Protocol Amendment 5, this study is a Phase 2 single-arm, open-label, multicenter, study to assess intrahepatic and peripheral changes of immunologic and virologic markers in response to a combination regimen containing JNJ-3989 and NA in chronic HBV-infected participants.

With the implementation of an urgent safety measure, as described in Protocol Amendment 5, JNJ-6379 has been removed as study intervention and the study will continue as a single-arm study. Participants randomized to Arm 1 had to stop JNJ-6379 treatment immediately but continue JNJ-3989 + NA treatment.

In addition, participants who provide separate consent may receive optional treatment with PegIFN- $\alpha$ 2a starting after the Week 40 biopsy (or after the optional leukapheresis if applicable) but before the Week 48 visit. The duration (either 12 or 24 weeks) will be at the investigator's discretion.

A target of 24 chronic HBV-infected male and female participants, 18-65 years (inclusive) of age will be enrolled in 2 panels, approximately 12 participants in each panel. Panel 1 will consist of participants who are HBeAg positive and not currently treated and Panel 2 will consist of participants who are HBeAg negative and virologically suppressed by entecavir (ETV), tenofovir disoproxil, or tenofovir alafenamide (TAF) treatment.

The study will be conducted in 3 phases for all participants: a screening phase (4 weeks), an open-label study intervention phase (48 weeks), and a follow-up phase (48 weeks). If necessary, eg, for operational reasons, the screening phase may be extended up to a maximum of 6 weeks on a case-by-case basis and in agreement with the sponsor. The duration of individual participation will be up to 102 weeks. Note that the follow-up period will be extended for participants who are receiving optional treatment with PegIFN- $\alpha$ 2a and who meet NA treatment completion criteria at the end of treatment with NA and PegIFN- $\alpha$ 2a to ensure all participants have at least one year of follow-up after NA treatment cessation. For those participants, the duration of individual participation may be extended up to 126 weeks.

Prior to Protocol Amendment 5, participants were randomized in a 1:1 ratio within each panel to receive one of the following interventions (ie, treatments) for 48 weeks:

- Intervention arm 1, combination regimen JNJ-3989+JNJ-6379+NA (target of 12 participants):

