  - 200 mg JNJ-3989 (SC injection once every 4 weeks [Q4W], with the last injection at Week 44), AND
  - 250 mg JNJ-6379 (tablets once daily [qd]), AND
  - NA: ETV, tenofovir disoproxil, or TAF (tablets qd)
- Intervention arm 2, combination regimen JNJ-3989+NA (target of 12 participants):
  - 200 mg JNJ-3989 (SC injection Q4W, with the last injection at Week 44), AND
  - NA: ETV, tenofovir disoproxil, or TAF (tablets qd)

As of Protocol Amendment 5:

- Participants who were randomized to study intervention with JNJ-6379 prior to Protocol Amendment 5, had to stop JNJ-6379 treatment immediately but will still receive the following interventions (ie, treatments) for 48 weeks:
  - 200 mg JNJ-3989 (SC injection Q4W, with the last injection at Week 44), AND
  - NA: ETV, tenofovir disoproxil, or TAF (tablets qd)
- New participants will enroll without randomization within each panel to receive the combination regimen JNJ-3989 + NA as study intervention for 48 weeks:

200 mg JNJ-3989 (SC injection Q4W, with the last injection at Week 44), AND

NA: ETV, tenofovir disoproxil, or TAF (tablets qd)

For participants who consented to receive optional PegIFN- $\alpha$ 2a, the PegIFN- $\alpha$ 2a treatment will be completed after 12 or 24 weeks at the investigator's discretion.

All participants will complete treatment with JNJ-3989 after a fixed duration of 48 weeks. If the NA treatment completion criteria (see "Study Intervention Completion at Week 48") are met based on clinical laboratory tests performed at Week 44, treatment with NA will also be completed at Week 48. In participants not meeting these criteria, NA treatment will continue during the follow-up phase. Participants who are receiving optional treatment with PegIFN- $\alpha$ 2a and who have not met NA treatment completion criteria at Week 48 may have NA treatment completion criteria assessed at the end of treatment with PegIFN- $\alpha$ 2a and stop NA if criteria are met.

All participants will have sparse PK sampling on Day 1 and at Weeks 4, 12, and 24 (and at early withdrawal). All participants who consent to participate in the intensive PK substudy (optional) will undergo intensive PK sampling at Week 4.

All participants will be monitored closely during the follow-up phase and, if applicable, should restart NA treatment in accordance with the NA re-treatment criteria mentioned below.

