### 1.3.3. Schedule of Activities – Optional PegIFN- $\alpha$ 2a Treatment

Participants who provide separate consent, may receive treatment with optional PegIFN- $\alpha$ 2a starting after the Week 40 biopsy (or after the optional leukapheresis if applicable) but before the Week 48 visit. The duration (either 12 or 24 weeks) will be at the investigator's discretion.

**In addition to the main schedules of activities (refer to Sections 1.3.1 and 1.3.2), the following visits and assessments will be performed for participants receiving PegIFN- $\alpha$ 2a.**

Phase		Optional PegIFN $\alpha$ 2a treatment				Comments
Additional visits	Before	Start	+2 wks	+4 wks	End (+12 or 24 wks)	
Study Day (relative to start of PegIFN $\alpha$ 2a treatment)		1	15	29	85 or 169	
ICF for PegIFN $\alpha$ 2a treatment	X					Participants must sign a separate ICF prior to the start of PegIFN <math>\alpha</math>2a treatment. Refusal to give consent for this optional treatment does not exclude a participant from participation in the study.
Exclusion criteria for PegIFN $\alpha$ 2a treatment	X					To be checked prior to the start of PegIFN <math>\alpha</math>2a treatment (refer to Section 5.2).
Administer PegIFN $\alpha$ 2a for 12 or 24 weeks		(Weekly)				All PegIFN <math>\alpha</math>2a administrations (on study visits and in between study visits) should preferably be done in the evening by self injection. If desired, participants can also choose to have the weekly administration of PegIFN <math>\alpha</math>2a performed on site irrespective of the time of day.
Dispense PegIFN $\alpha$ 2a		(Every 4 weeks)				Participants will receive PegIFN <math>\alpha</math>2a supply for self administration at home in between study visits.
Study intervention accountability			X	X	X	
Body weight and Symptom directed physical examination		X	X	X	X	
Ophthalmic examination	X	(As applicable)				Periodic ophthalmologic examinations during PegIFN <math>\alpha</math>2a treatment are at the investigator's discretion. Any patient who develops ocular symptoms should receive a prompt and complete eye examination.
Injection site reactions for PegIFN $\alpha$ 2a		(At every visit)				
Hematology			X	X		
Blood chemistry (including liver function tests)				X		
Blood sampling for HBV DNA		X			X	
Blood sampling for HBsAg (quantitative)		X			X	
Blood sampling for HBeAg (quantitative)		X			X	

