**Table 5: PegIFN- $\alpha$ 2a Hematological Dose Modification Guidelines**

Laboratory Values	Recommended Dose
ANC <750 cells/mm 	Reduce to 135 $\mu$ g
ANC <500 cells/mm 	Discontinue treatment until ANC values return to more than 1,000 cells/mm  . Reinstitute at 90 $\mu$ g and monitor ANC.
Platelet <50,000 cells/mm 	Reduce to 90 $\mu$ g
Platelet <25,000 cells/mm 	Discontinue treatment

ANC: absolute neutrophil count

Source: Pegasys USPI and SmPC

For participants who prematurely discontinue PegIFN- $\alpha$ 2a, treatment with PegIFN- $\alpha$ 2a may be restarted according to the recommendations from the locally approved prescribing information for PegIFN- $\alpha$ 2a.

### 6.6.1. Study Intervention Completion at Week 48

With the implementation of Protocol Amendment 5, all participants had to stop JNJ-6379 treatment immediately.

Participants will complete treatment with JNJ-3989 after a fixed duration of 48 weeks. If all of the below criteria are met based on clinical laboratory tests performed at Week 44, treatment with NA will also be completed at the next scheduled visit (ie, Week 48):

- The participant has ALT <3x ULN, AND
- The participant has HBV DNA <LLOQ, AND
- The participant is HBeAg negative, AND
- The participant has HBsAg <10 IU/mL.

**Note:** In case of ALT elevation  $\geq 3$ x ULN at Week 44 the investigator must consider different potential causes of increased ALT to ensure appropriate work up and management as needed. If the ALT elevation is unrelated to HBV activity and/or <3x ULN by Week 48, NA completion may be considered at the discretion of the investigator and in consultation with the sponsor.

Participants who do not meet the above criteria at Week 48 should continue NA treatment during the 48-week follow-up phase. Participants who are receiving optional treatment with PegIFN- $\alpha$ 2a and who have not met NA treatment completion criteria at Week 48 may have NA treatment completion criteria assessed at the end of treatment with PegIFN- $\alpha$ 2a and stop NA if criteria are met.

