### **6.6.2. NA Re-treatment Criteria and Monitoring after Stopping of NA**

Participants who meet the NA treatment completion criteria outlined in Section [6.6.1](#) will be monitored closely during the follow-up phase.

After stopping NA treatment, participants should be monitored as follows:

- Regular monitoring visits will be every 4 weeks during the follow-up phase in accordance with the [Schedule of Activities](#).

- A post-treatment HBV DNA value of >20,000 IU/mL should trigger re-testing of ALT/AST, HBV DNA, and total and direct bilirubin within a maximum of 7 days from receipt of the data and further repeats as necessary (ie, weekly until HBV DNA returns to <20,000 IU/mL).
- A post-treatment HBV DNA value of >2,000 IU/mL (but <20,000 IU/mL) should trigger a re-test within 14 days from receipt of the data and further repeats as necessary (ie, every other week until HBV DNA returns to <2,000 IU/mL).
- A post-treatment ALT value of >5x ULN should trigger re-testing of ALT, AST, ALP, total and direct bilirubin, INR, albumin, and HBV DNA on a weekly basis until ALT and AST levels have returned to <5x ULN.

After stopping NA treatment, participants should re-start NA treatment:

- Immediately with signs of decreasing liver function based on laboratory findings (eg, INR, direct bilirubin) or clinical assessment (eg, ascites, hepatic encephalopathy),
- Immediately with an HBV DNA value of >100,000 IU/mL (irrespective of confirmation and/or ALT increase).
- With confirmed post-treatment HBeAg seroreversion (HBeAg positive after it was negative at NA completion)
- With confirmed\* post-treatment increases in HBV DNA >2,000 IU/mL and ALT >5x ULN
- With confirmed\* post-treatment increases in HBV DNA >20,000 IU/mL.

*\* At least 4 weeks apart frequency of visits as described above*

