In addition, participants who provide separate consent may receive optional treatment with PegIFN- α 2a starting after the Week 40 biopsy (or after the optional leukapheresis if applicable) but before the Week 48 visit. The duration (either 12 or 24 weeks) will be at the investigator's

discretion. This will allow investigation of whether addition of PegIFN- α 2a for 12 or 24 weeks may increase the participant's chance to achieve HBsAg loss.

All participants will complete treatment with JNJ-3989 after a fixed duration of 48 weeks. Treatment with NA will also be completed at Week 48 except for participants not meeting the NA treatment completion criteria (outlined in Protocol Section 6.6.1). In participants not meeting these criteria, NA treatment will continue during the follow-up phase. Participants who are receiving optional treatment with PegIFN- α 2a and who have not met NA treatment completion criteria at Week 48 may have NA treatment completion criteria assessed at the end of treatment with PegIFN- α 2a and stop NA if criteria are met.

[figure not shown]
In case of premature discontinuation of study agent JNJ-3989 (before Week 48), follow-up assessments should be obtained until 48 weeks after End Of Study Intervention (EOSI) unless the participant withdraws consent. Participants who withdraw consent will be offered an optional safety follow-up visit.

The SAP will use throughout the document the following definitions:

- *Study treatment* refers to JNJ-6379, JNJ-3989, NA (either ETV, TD, or TAF), and PegIFN- α 2a.
- *Study agent* refers to JNJ-6379 and JNJ-3989
 - *Arm* refers to:
 - Arm 1: JNJ-3989+JNJ-6379+NA
 - Arm 2: JNJ-3989+NA

A schematic overview of the study is presented in [Figure 1](#) (Prior to Protocol Amendment 5) and in [Figure 2](#) (As of Protocol Amendment 5).

[figure not shown]
Figure 1: Schematic Overview of the Study – Prior to Protocol Amendment 5

ETV: entecavir; N: number of participants; LB: (planned) liver biopsy; NA: nucleos(t)ide analog; Q4W: once every 4 weeks; qd: once daily; TAF: tenofovir alafenamide; TD: tenofovir disoproxil; QW: once weekly

* Participants who provide separate consent may receive optional treatment with PegIFN- α 2a starting after the Week 40 biopsy (or after the optional leukapheresis visit if applicable) for a duration of either 12 or 24 weeks at the investigator's discretion.

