- 0 (No) = otherwise

^{**} Confirmed means that the criterion should be fulfilled at 2 or more consecutive time points or at the last observed time point.

The virologic and clinical flares will be assessed only off-treatment, while biochemical flares will be identified on-treatment and off-treatment, respectively. On-treatment virologic flares are described as virologic HBV breakthrough in Section 5.4.2.7.

On-treatment will be defined as the time periods in which the participant receives any of the study interventions (JNJ-3989 or JNJ-6379 or NA or PegIFN- α 2a). Off-treatment will be defined as the

periods when the participants do not receive any of the study interventions (JNJ-3989, JNJ-6379, NA, and PegIFN- α 2a).

The incidence rate will be calculated and summarized for each type of on-treatment or off-treatment flares (virologic, biochemical and clinical) separately, as well as the overall incidence of participants experiencing at least one flare, regardless of type. Additionally, for each participant the total number of flares the participant experienced will be counted by type. Such counts will be used to summarize the distribution of the total number of flares by type and by study panel.

For on-treatment biochemical flares, the incidence of flares causing treatment discontinuation will be summarized. Further, for off-treatment flares, the count and percentage of participants who experienced a flare followed by NA re-treatment will be summarized by flare type. Similarly, the incidence of flares followed by the achievement of HBsAg seroclearance (at any time) will be summarized by flare type.

Flares that are associated with signs of liver decompensation will be provided in a listing.

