5.4.2.7. HBV Virologic Breakthrough

5.4.2.7.1. Definition

HBV virologic breakthrough is defined as having a confirmed on-treatment HBV DNA increase by $>1 \log_{10}$ from nadir level (lowest level reached during treatment) in participants who did not have on-treatment HBV DNA level $< \text{LLOQ}$ or a confirmed on-treatment HBV DNA level $>200 \text{ IU/mL}$ in participants who had on-treatment HBV DNA level $< \text{LLOQ}$. Confirmed HBV DNA increase/level means that the criterion should be fulfilled at 2 or more consecutive time points or at the last observed on-treatment time point.

On-treatment will be defined as the time period in which the participant receives any of the study interventions (JNJ-3989 and/or JNJ-6379 and/or NA and/or PegIFN- α 2a).

The number and proportion of participants who experience a virologic breakthrough will be summarized descriptively by analysis phase.

The number and proportion of participants who experience a virologic breakthrough followed by on-treatment biochemical flare will be summarized descriptively.

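### PegIFN participants who stop NA at Week 48 remain on-treatment until PegIFN ends, so an HBV DNA rebound that resolves or is re-treated in that window counts as breakthrough, never as a virologic or clinical flare

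*SAP*

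**What the plan says.** **NA and PegIFN timing.** Optional PegIFN is given "starting after the Week 40 biopsy (or after the optional leukapheresis if applicable) but before the Week 48 visit" (Protocol 1.3.3). On its length, the Protocol Synopsis says: "The duration (either 12 or 24 weeks) will be at the investigator's discretion". For participants who meet the Week 44 criteria, "treatment with NA will also be completed at Week 48" (Protocol Synopsis, Overall Design). Protocol 6.6.1 makes no exception for participants on PegIFN. Only those who have not met the criteria may be reassessed when PegIFN ends. SAP 1.2 agrees: "Treatment with NA will also be completed at Week 48 except for participants not meeting the NA treatment completion criteria". Protocol 6.6.2 introduces its rules with "After stopping NA treatment, participants should be monitored as follows" and treats HBV DNA and ALT values from that point as post-treatment.

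**On- and off-treatment.** SAP 5.1.3 ends the on-treatment period at the latest of last NA dose + 2 days, last PegIFN dose + 10 days and last JNJ-3989 dose + 28 days. SAP 5.4.2.6.1 restricts two of the three flare types: "The virologic and clinical flares will be assessed only off-treatment, while biochemical flares will be identified on-treatment and off-treatment, respectively". It refers HBV DNA rises on treatment to the breakthrough section. There, SAP 5.4.2.7.1 says: "On-treatment will be defined as the time period in which the participant receives any of the study interventions", and it names PegIFN among those interventions.

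**The concern.** The protocol times its post-treatment rules from NA stop, and the SAP times flares from the last of all study interventions. For most participants who meet the criteria the two coincide at Week 48. For a PegIFN participant who stops NA at Week 48 they can differ by months.

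A severe flare after NA withdrawal in another study led Amendment 5 to tighten monitoring and revise the NA re-treatment criteria (Protocol 4.2). The virologic and clinical flare endpoints are where such events should appear. Under the SAP rule, some will appear only in the breakthrough table, alongside HBV DNA rises in participants still taking NA. Those are two different events.

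**Working it through.** The plan gives no figure to reproduce. The check compares the definitions and then does calendar arithmetic on the protocol's own study days.

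**Which drug keeps the participant on-treatment after Week 48?**
- NA: stopped at Week 48 (Day 337), so cover ends 2 days later.
- JNJ-3989: last injection at Week 44 (Day 309). 309 + 28 = Day 337, so it adds nothing beyond Week 48.
- PegIFN: the only component that extends the period. This holds under SAP 5.1.3 and under the shorter definitions in 5.4.2.6.1 and 5.4.2.7.1.

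**How is a rebound classified in that window?**
- NA completion requires HBV DNA <LLOQ (Protocol 6.6.1), so the >200 IU/mL branch of breakthrough applies. A confirmed value above 200 IU/mL is a breakthrough.
- A virologic flare cannot exist on-treatment, and a clinical flare needs a virologic flare. Both are therefore zero.
- An ALT/AST rise that meets the thresholds is an on-treatment biochemical flare.
- If NA is restarted before PegIFN ends, the participant stays on-treatment, and the episode is missing from the summary of off-treatment flares followed by NA re-treatment.
- If the rebound resolves before PegIFN ends, the later off-treatment values no longer show it.

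Hypothetical case: NA stopped at Week 48 with HBV DNA <LLOQ, PegIFN running to Week 66, HBV DNA 5,000 IU/mL at Week 56 and 30,000 IU/mL at Week 60, NA restarted at Week 60. The rule gives one breakthrough, no virologic flare and no clinical flare.

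**What if the rebound persists untreated past PegIFN?** The last on-treatment HBV DNA is then ≥LLOQ, so Derivation 2 applies (a rise of more than 1 log10). Its reference is open to two readings:
- EOT as in SAP Table 2, the last open-label visit, about Week 48. If HBV DNA there is still <LLOQ, it is imputed at 5 or 15 IU/mL (SAP Table 3). log10(201/5) = 1.60 and log10(201/15) = 1.13, so the episode counts as a flare with a late start date, and also as a breakthrough.
- End of treatment as the last on-treatment value. From 201 IU/mL, a further rise above 2,010 IU/mL is needed, so the episode may never count.

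**How long is the window?** The last weekly dose falls at start + 77 days (12 weeks) or start + 161 days (24 weeks). Window = start + 77 (or 161) + 10 − 337, in days; percentages are of 48 weeks (336 days).

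| PegIFN start | 12-week course | 24-week course |
|---|---|---|
| Day 281 (nominal Week 40) | 31 d = 4.4 wk (9%) | 115 d = 16.4 wk (34%) |
| Day 336 (day before Week 48) | 86 d = 12.3 wk (26%) | 170 d = 24.3 wk (51%) |
| Day 253 (biopsy 4 weeks early) | 3 d = 0.4 wk | 87 d = 12.4 wk |

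Counted to the PegIFN end visit (start + 84 or 168 days), without the 10-day rule, the first two rows give 4.0 to 11.9 and 16.0 to 23.9 weeks.

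**Can a rebound be confirmed there?** Counting follow-up weeks from Week 48, the first two rows contain between 2 scheduled HBV DNA visits (Follow-up Weeks 2 and 4) and 7 (Follow-up Weeks 2 to 24). Two consecutive values can be observed, and a single value at the last on-treatment time point also counts as confirmed.

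**The case against.** **The rule is deliberate.** The SAP version history says the definition was added because the earlier logic ignored which agent ended last. PegIFN is a study intervention, and Protocol 2.3.1.2 credits it with direct antiviral effects, so calling a rise on PegIFN a breakthrough is coherent. The post-treatment wording in Protocol 6.6.2 governs monitoring and re-treatment, not endpoint derivation. This stands as a reason to keep the definition for other endpoints. It does not justify merging rebounds off NA with breakthrough on NA.

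**The events are not lost.** Breakthrough is reported by analysis phase, and breakthrough followed by an on-treatment biochemical flare is summarised. The ALT rise enters the overall incidence of any flare. NA re-treatment is summarised without regard to PegIFN (SAP 5.4.2.4.7), and individual profiles are plotted. All of this is correct, but none of these summaries separates participants who had stopped NA from those still on it.

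**PegIFN itself can raise ALT** (Protocol 2.3.2.1), so scoring clinical flares during PegIFN mixes causes. This also stands, and it is why such events need their own row.

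**A stronger reading to avoid.** A reader might infer that flare rates in general are understated, and that the PegIFN yes/no comparison must show fewer flares on PegIFN. The documents do not support that. Biochemical and overall flare incidence still include the ALT rise, persistent rebounds can count under Derivation 2, and subgroup analysis of key secondary endpoints is only optional (SAP 5.4.3).

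**Conclusion.** The point holds for a defined set of cases: PegIFN participants who stop NA at Week 48 and have a confirmed HBV DNA rebound that resolves or is re-treated before PegIFN ends. For them the virologic and clinical flare count is zero by definition, and the event is pooled with breakthrough on NA. For rebounds that outlast PegIFN, the count and start date depend on a reference value that the SAP leaves ambiguous.

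The window is about 9-26% of 48 weeks for a 12-week course and 34-51% for a 24-week course. This assumes a start between nominal Week 40 and Week 48, weekly dosing without delays, and the SAP 5.1.3 rule of 10 days from the last dose. An early biopsy can shorten the minimum to about 0.4 or 12.4 weeks.

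The documents do not give the number affected. As an assumption only, the 19.1% completion rate quoted for the 200 mg arm of another study (Protocol Appendix 10, Amendment 4) applied to 24 participants gives 0.191 × 24 = 4.6, before PegIFN uptake and rebound are considered. The endpoints are secondary and descriptive, and the primary endpoint is untouched. The change is still worth making, because with so few participants one reclassified event visibly changes a flare table.

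**What to change.** Keep the existing on-treatment definition for other endpoints. Then:

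- For virologic and clinical flares, add a derivation whose at-risk period starts at the last NA dose + 2 days, whether or not PegIFN continues.
- Use the last HBV DNA value on NA both to choose between Derivations 1 and 2 and as the reference for the log10 increase. In this added derivation, that removes the ambiguity about end of treatment.
- Report events during PegIFN in a separate flagged row.
- Split the virologic breakthrough table into events while on NA and events after NA stop during PegIFN, and include the latter in the summary of flares followed by NA re-treatment.

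The cost is one date derivation and some extra table rows, using data already collected. No clinical rule changes.
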